3. To identify potential effects of health insurance on public health facilities (e.g., hours and drug availability; subjective and objective quality indicators).

 To contribute to the body of knowledge on health insurance in Cambodia and in developing countries more broadly.

3. Research Design

We will use a mix of qualitative and quantitative methods, including both in-depth interviews of SKY employees, health care providers and households and a large household survey.

The large household survey will measure the impact of insurance on rural Cambodians. To overcome the key obstacle to causal inference—that those who choose to purchase insurance typically differ in many observable and unobservable ways from those who do not—we will implement a randomized controlled trial that allows us to identify the impact of health insurance independently from all other factors that may affect a household's decision to take up insurance. No household will be denied access to insurance. Rather, by subsidizing the premium of a randomly selected group of households, we can estimate the effect of insurance on households without substantially altering the existing SKY program. The study design will also enable us to examine characteristics of the groups that buy or decline insurance at different prices. Using data from the baseline survey, we will examine the characteristics (in particular, health status and prior health care utilization) of those who choose to purchase health insurance at different prices. Using data from the follow-up survey, we will also compare the utilization rates of people who buy insurance at different prices, and compare the dropout rates of those who utilize facilities at different rates. Both techniques allow us to estimate the extent and nature of self-selection.

The randomized evaluation will be implemented as SKY visits villages to promote insurance. When the SKY program first rolls out into a region, SKY holds a village meeting to describe the insurance product to prospective customers. At

the end of each meeting, SKY will hold a Lucky Draw lottery in which a random subset of households receives coupons for discounts on the insurance premium.

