The randomization of premiums will provide a discount to some households. Of households that attend the village meeting, 20% of households, up to a maximum of 12 households per village, will win a coupon for 5-months free insurance in the first 6-month cycle, with the option to renew for a second 6-month cycle with a coupon for 3-months free. The remaining households in attendance at the meeting will be entitled to a coupon for a 1-month discount on insurance, which is the usual policy for the SKY program. SKY will be holding village meetings in Takeo, Kandal, and Kampot provinces over the course of the thirteen months from November 2007 to December 2008 (roughly the period during which the baseline survey will be administered). Table 1 shows an approximation of the distribution of the targeted sample across regions. The column "Total Meetings Held" indicates the number of village meetings SKY plans to hold in each district or province and "Total Lucky Draws" indicates the number of Lucky Draws held in the given district. The final column, "% of Villages Surveyed", indicates the approximate percentage of the sample that will come from each area. Note that we will hold Lucky Draws at most village meetings in 2008. We will only survey villages in which we hold a Lucky Draw.

				Total	Total	% of Villages	
				Meetings	Lucky	Surveyed	
				Held	Draws		
Takeo Province			128	128	51%		
Ang Roka village	s (older	villages)		32	32	13%	
Kirivong villages			48	48	19%		
Donkeo villages				48	48	19%	
Kandal Province	74	72	29%				
Koh Thom village	es			74	72	29%	
Kampot Province	50	50	20%				
Kampot villages				50	50	20%	
All Villages				252	250	100%	

Table 1: Targeted Regions

In addition to the randomized intervention, we will also be studying the effect of SKY on the quality and functioning of public health facilities. The fact that higher quality facilities are targeted by SKY means that there can be no valid control group in a longitudinal study, but we will use several methods to measure changes in health center quality over time that will allow us to gain some insight into the impact of SKY.

4. Sampling Strategy

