For the quantitative survey, the main evaluation sample will consist, roughly, of half coupon winners and half non-winners. More precisely, we will interview all large coupon winners, and randomly select an equal number of small coupon winners to interview. In addition, to address the question of selection into insurance, we will oversample households that purchased insurance from the population of small coupon winners. In total, our sample of approximately 5,200 households will consist of approximately 46% large coupon winners and 54% small coupon winners. For the quantitative survey, the main evaluation sample will consist, roughly, of half coupon winners and half non-winners. More precisely, we will interview all large coupon winners, and randomly select an equal number of small coupon winners to interview. In addition, to address the question of selection into insurance, we will oversample households that purchased

insurance from the population of small coupon winners. In total, our sample of approximately 5,200 households will consist of approximately 46% large coupon winners and 54% small coupon winners¹.

The survey team will interview households between two and seven weeks after the village meeting². An Evaluation Representative will attend each village meeting to help run the Lucky Draw lottery. At the end of each village meeting the Evaluation Representative will randomly select a number of the small coupon winners to be interviewed. SKY Insurance Agents will visit these households, as well as all large coupon households, before the 21st of the month. Once all households have had the opportunity to purchase insurance, we will interview these sampled households. Table 2 offers a breakdown of the interview sample.

	Large coupon wi	inners S	Small coupo	n winners	Additional small coupon	Total
	(100% sampled)		(25% sampled) buyers		(50% sampled)	
	1	2	3	4	5	6
	Total	Buyers (est.)	Total	Buyers (est.)	(Estimated)	(Estimated)
Per meeting	9.5	3.8	9.5	0.57	1.8	20.8
Total	2,375	950	2,375	143	453	5,203

Table 2: Quantitative survey sample

Notes: We assume 250 village meetings. Based on the results from the pilot test in 2007, we assume 40% of large coupon winners purchase SKY and 6% of small coupon winners purchase SKY.

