5.2. Village Leader Interview

In each village, we will interview the village chief or village leader in order to collect general village-level information, including the location of all local health facilities (public, private, pharmacies, traditional healers, etc.), recent villagelevel shocks (drought, flood, epidemics, etc.), availability of lending institutions, seasonal access to roads and price and availability of paid transportation. Because the randomization is at the household level, the information garnered from the village leader will be of greatest use in the selection study (e.g., testing if villages far from regional hospitals have lower take-up), in assessing the external validity of the evaluation, and potentially in estimating the effect of insurance in villages with different characteristics.

³ See previous footnote: the timelag between village meetings and interviews will be longer for households attending earlier village meetings.

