6.1. Statistical Methods

To estimate the causal effect of health insurance on household health and economic outcomes, we will implement a number of estimators. The overall econometric technique is to generate multiple estimates of the effect of insurance on the outcomes of interest, thus allowing us to construct a credible range of the estimated program effect. To begin with, we will construct a lower bound for the program effect the Intention-to-Treat effect. Here, outcomes at baseline will be differentiated from outcomes in the follow-up, across large and small coupon winners. This estimate provides a credible lower bound for the true program effect, because many of the large coupon winners will not take up insurance, while some of the small coupon winners will, yielding an underestimate of the true program effect. Formally, we will run a regression that includes a vector of individual fixed effects (individuali) to absorb characteristics of the household or individual, observed or unobserved, that do not change over time and a vector of year fixed effects (year t) to control for changes over time that affect all individuals (or households). We can also control for

This section outlines our methodology for achieving each goal. For objectives 1 through 3, we include a list of indicators that we plan to measure using our survey instruments. Note that the final list of indicators will depend on pre-test results, and on the power we have to measure SKY impacts using each indicator with the given study design.

Methodology for Objective 1: The Causal Effect of Health Insurance

J and I time-variant individual- and household-level covariates (Xjt and Zjit) that might affect health, health care utilization, and other outcomes, e.g., current household income. Thus, we can estimate:

Yjivt = β postit * large-couponi + γ postit + Σ li=1 α Xit + Σ Jj=1 δ Zjit + individualj+ yeart + Uvt + ϵ jivt

In this specification, postit indicates follow-up observations, Uvt represents village-level shocks collected in the village leader survey, and ɛjivt is a random error term representing individual variation from the mean. The coefficient β is the difference-in-differences estimate of the effect of being offered a high-value coupon. Outcome indicators (the Yjivt in the equation above) for Objective 1 are listed below.

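### The ITT equation handles village-specific change over time only through leader-reported shocks; village-by-round indicators would match the per-village lottery and are a low-cost safeguard.

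*Protocol*

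**What the plan says.** Protocol section 3 holds a separate draw in every village: at "the end of each meeting, SKY will hold a Lucky Draw lottery". The large coupon goes to "20% of households, up to a maximum of 12 households per village". Section 5.2 confirms the unit: "Because the randomization is at the household level".

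For the main evaluation sample, section 4 says "we will interview all large coupon winners, and randomly select an equal number of small coupon winners to interview". The draw takes place at the meeting, where "the Evaluation Representative will randomly select a number of the small coupon winners to be interviewed". Table 2 shows 9.5 of each group per meeting, but its column heading gives a sampling fraction of 25% for small-coupon winners.

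The ITT equation in section 6.1 contains individual fixed effects, year effects common to all villages, optional time-varying covariates, and a village-by-time term: "Uvt represents village-level shocks collected in the village leader survey". Neither that equation nor equations (2) to (7) of the Statistical Appendix has a village-by-round effect. Part d of the Appendix says that clustering by village and by household will be taken into account.

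**The concern.** A draw made within each village supports comparison within each village. Individual effects remove whatever is constant in a village. Year effects remove whatever changes alike everywhere. What is left is change peculiar to one village between rounds, and the equation picks this up only as far as a leader reports it.

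That measure is uncertain on the protocol's own terms. Section 5.1 sets three rounds for the household survey, while section 5.2 states no repeat for the leader interview, so a time-varying Uvt may not be measurable. Section 5.2 gives the main uses of leader data as the selection study, external validity and effects by type of village; ITT adjustment is not among them. Village meetings, and so the baseline, roll over November 2007 to December 2008, and minor illness is recalled over four weeks. A common year effect therefore cannot represent conditions in one village's own recall window.

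If the large-coupon share is the same in every village, unreported shocks fall equally on both groups and cancel. If shares differ, the shocks enter the coupon contrast as noise. They enter as bias if the share is related to the village trend.

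**Working it through.** **Plan's own figure.** Table 2: 9.5 × 250 = 2,375 per coupon group; 2,375 + 2,375 + 453 = 5,203; 2,375 / 5,203 = 45.6% large coupon. This reproduces. The protocol gives no power, standard deviation or intraclass correlation to check against.

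**Set-up.** Take two rounds in first differences, with the variance of the change set to 1 and a share ρ of it common to the village (assumed 0 to 0.20). Village v has n_v households and large-coupon share p_v; overall these are N and p.

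- Without indicators: Var = (1−ρ)/[N p(1−p)] + ρ Σ[n_v(p_v−p)]² / [N p(1−p)]²
- With indicators: Var = (1−ρ)/Σ n_v p_v(1−p_v)

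**Exact 1:1 in each village (4,750 households).** Every p_v = p = 0.5, so the second term is zero and the two variances are equal at every ρ. At ρ = 0.10 the SE is √(0.9 × 4 / 4,750) = 0.0275. Simulation gave a village-clustered SE of 0.02747 with and without indicators, and the same estimate. Residual degrees of freedom fall from 4,748 to 4,499, a loss of 249.

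**Hand check, 20% random attrition (assumed).** Per village, the variance of the difference in group counts is 2 × 9.5 × 0.8 × 0.2 = 3.04, and n = 15.2. Then n p(1−p) = 3.8, the within-village sum is about 3.8 − 3.04/(4 × 15.2) = 3.75, and [n_v(p_v−p)]² averages 3.04/4 = 0.76. At ρ = 0.20, each variance multiplied by the number of villages is:

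- without: 0.8/3.8 + 0.2 × 0.76/3.8² = 0.2211
- with: 0.8/3.75 = 0.2133

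The ratio is 0.965, against 0.966 from the full calculation.

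**Variance with indicators divided by variance without:**

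| Setting (assumed) | ρ = 0 | ρ = 0.10 | ρ = 0.20 |
|---|---|---|---|
| Exact 1:1 | 1.000 | 1.000 | 1.000 |
| 10% attrition | 1.006 | 0.995 | 0.982 |
| 20% attrition | 1.014 | 0.992 | 0.966 |
| Person level, household-size SD 2, 10% attrition | 1.016 | 0.890 | 0.770 |
| Flat 25% of small-coupon winners | 1.014–1.024 | 0.942–0.969 | 0.857–0.919 |

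The person-level row uses a mean household size of 4,392/917 = 4.8, from the programme figures in the introduction. It assumes no correlation within households, so its gain is an upper limit.

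**Flat 25% reading.** The cap binds above 12/0.20 = 60 attendees. Up to 60, 25% of the other 80% equals the winners' 20%, so 25% and an equal number agree. At 100 attendees there are 12 winners and 0.25 × 88 = 22 small-coupon households, a share of 12/34 = 35%. The table row assumes mean attendance near 58 with an SD of about 22 or 30.

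The share now depends on attendance, so bias is possible: bias = c √ρ Σ n_v(p_v−p)z_v / [N p(1−p)]. Here z_v is standardised attendance and c is the correlation of village trend with attendance. For c = 0.3 to 0.5 and ρ = 0.05 to 0.20, its size is 0.015 to 0.07 SD of the change, against an SE near 0.03. A separate simulation with mean attendance 50 and 15% loss gave roughly 0.01 to 0.045 SD. Indicators remove it.

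**The case against.** The strongest reply is that nothing stated is shown to be wrong. Under the sampling in the text of section 4, groups are equal in each village and indicators change nothing. The cap limits winners and their matched sample alike, so by itself it does not unbalance the shares. Random attrition moves the variance by only +1.4% to −3.4%. The bias figures need both the flat 25% reading and an assumed link between village trend and attendance. The Appendix equations are illustrative, with an open controls term, and stratum indicators may be specified in an SAP that was not available.

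Most of this stands, and it rules out two stronger readings that a reader might infer.

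- *That the ITT estimate is biased as planned.* The documents do not support this: individual effects absorb stable village differences, and equal sampling makes the coupon orthogonal to village shocks.
- *That the planned standard errors misfit the design.* Part d of the Appendix already plans a correction for village and household clustering, so figures for unclustered errors do not describe this plan.

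It would also be wrong to say that leader reports miss whole kinds of obvious shock: section 5.2 names drought, flood and epidemics. Nor do the extra small-coupon buyers help the argument. They are added for the selection question, and village indicators would not cure selection on purchase if they entered the ITT.

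What the reply does not remove is that section 6.1 writes out an equation resting on a measure with no stated follow-up collection, and that exact balance will not survive to the analysed data.

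**Conclusion.** The point holds as a low-severity improvement. The equation does not condition on the strata within which the lottery is drawn, and its substitute may not be measurable at follow-up.

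The size depends on how far coupon shares differ between villages. There is no effect at exact 1:1. The variance gain is up to about 3% for household outcomes with 20% attrition, about 8% to 14% at ρ = 0.20 under the flat 25% reading, and at most 23% for person-level outcomes. Bias of 0.015 to 0.07 SD is possible only under the flat 25% reading with village trends related to attendance. The LATE divides by a first stage of 0.40 − 0.06 = 0.34, so any such bias would be multiplied by about 2.9 there; the standard error scales by about the same factor.

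The village correlation, attrition, household-size spread, attendance distribution and trend–attendance correlation are all assumptions, because the protocol gives none of them.

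**What to change.** In section 6.1, replace Uvt with village-by-round indicators. Put the same indicators among the controls of the first stage (2), the second stage (3) and the reduced form (4). Keep the clustering correction of Appendix part d. Keep leader-reported shocks for the selection and external-validity work of section 5.2. Separately, reconcile the equal-number rule in section 4 with the 25% heading in Table 2 for villages above the cap.

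The change is to analysis wording only. Coupons vary within villages, so the effect stays identified. The cost is about 249 degrees of freedom per follow-up round, and roughly 0 to 2.4% of variance if village shocks are absent.

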6.2. Economic Outcomes

If successful, SKY health insurance will have the following economic effects: (a) lower health-related spending; (b) lower health-related debt; (c) fewer cases of asset sales, savings and decreased investment; (d) less lost income due to illness. This section describes the indicators we will use to measure these economic impacts.

6.2.1. Indicators for health-related spending

If we implement logbooks on a large scale, we will collect daily data on health incidents.

In the household survey, we will collect data on all health incidents in the last 4 weeks.

In addition, we will collect data using a 12- month recall period for "major" health incidents. A health incident will be defined as "major" if it meets one of the following definitions:

1. the individual was unable to perform daily activities for multiple consecutive days

2. treating the health incident was expensive (using some objective measure)

3. involved an overnight stay at a health facility

We will ask about health incidents by individual, not simply by household. This will allow us to assess the effect of insurance on intra-household health care disparities. Indicators include:

• Expenditure on drugs; non-drug treatments and exams (e.g., surgery, shots, etc.); overnight stays; other services (e.g., "thank you" payments); transport to health care providers

• Total cost of health-related expenditure, broken down by provider: public facilities (health center, referral hospital, provincial hospital); private doctor or provider; traditional healer; pharmacist; other health care provider

Specific to large expenditure (within the last 12 months):

· Amount spent on funeral expenses (if relevant)

Amount spent per month treating chronic illnesses or symptoms

• Amount spent on preventative care (immunizations, prenatal care etc.)

6.2.2. Health-related debt

Our qualitative research leads us to expect that households typically incur debt to cover health expenditure before selling off productive assets. Thus, health insurance has the potential to substantially reduce debt burdens after illness or injury. In the household survey we will use several indicators to measure these impacts:

• % of households with outstanding debt

 Amount of outstanding debt, including amount of debt specifically incurred from health expenses

 % of households paying high interest rates (e.g., > 8% / month) on existing debt

 % of households taking out a loan to pay for a healthrelated expense in the past 12 months

6.2.3. Asset sales, savings and decreased investment

Severe health shocks may lead households to sell assets, including productive assets such as livestock. Related to this is disinvestment in human capital, for example, if children are pulled out of school to care for the ill. One effect of insurance may be to reduce the amount of disinvestment upon experiencing a health shock; another may be that the household will reduce the amount of precautionary savings. To measure the impact of insurance on the sale of assets, changes in savings and changes in investment, we will collect information on:

• % of households that sold any type of asset, and % of households that sold a productive asset (animal, load- bearing animal, farm equipment, farmland, other land etc.) This question will also be asked in relation to specific health-related expenses or debts.

• % of households using savings to pay for health care, as well as the type of savings (e.g., gold, jewelry, etc.)

 \cdot % of households decreasing child school hours due to health shocks

 \cdot % of households increasing child labor hours to pay for health care expenses

6.2.4. Income lost due to illness

To measure the impact of insurance on income lost due to

6.3. Health Outcomes

To estimate the causal effect of health insurance on health outcomes, we will examine (a) the frequency, duration and severity of health incidents; (b) perceived health; (c) objective measures of health.

6.3.1. Frequency, duration and severity of health incidents

In the household survey and logbooks, to measure the impact of insurance on frequency, duration and severity of health incidents, we will collect:

• % of individuals with any illness in the last 4 weeks

• % of individuals with a major health incident in the last 12 months (defined above)

• % of individuals with a chronic illness

 Average duration of illness (measured by number of days an individual could not perform normal activities due to illness)

6.4. Health Care Utilization

We expect health insurance to have an impact on the following health-seeking behaviors: (a) treatment and choice of provider when ill; (b) preventive health care; (c) knowledge of appropriate preventive health behavior. We will use the following indicators to measure these impacts.

6.4.1. Treatment and choice of provider when ill

illness we will use the following indicators (collected for each household member):

· Days unable to perform usual activities

· Days unable to perform usual income-producing activities

 (Estimated) Implied income lost (equal to daily wage * lost work days)

6.3.2. Perceived health

Using the large-scale sample survey, we will ask the respondent to evaluate the general level of health of each household member. We will construct:

• % of individuals reporting poor health

% of individuals whose health has deteriorated in the last
12 months

